COVER PAGE

Study Title: Evaluation of adherence and outcomes in children with functional constipation after implementing a constipation action plan

NCT: *pending*

Date of Document: 18 October 2016

Study Protocol Title

Evaluation of adherence and outcomes in children with functional constipation after implementing a constipation action plan

Principal Investigator, Research Team, and Study Site

Principal investigator: [name] [name] PhD

Co-Investigator: [name], DO

[contact] [contact]

Address: [name]

Study site: Nemours/A.I. DuPont Hospital for Children

Study Title

Evaluation of adherence and outcomes in children with functional constipation after implementing a constipation action plan

Study Population

Children are eligible to participate in the study if they are otherwise healthy children whose primary language is English with no conditions that would predispose them to develop constipation, between the ages of 3 and 8 years of age and meet the ROME IV criteria for functional constipation.

Study Agent and Intervention Description

Implementation of a Constipation action plan tool: a document describing step by step what needs to be done in response to the patient's daily symptomatology of constipation.

Primary Objective

1. To assess compliance in pediatric patients with functional constipation that have been provided a constipation action plan plus educational information.

Outcome measures: compliance

Sticker reward chart review at 3 month visit in addition to constipation/adherence questionnaire at initial visit, 1 month telephone encounter and 3 month follow up visit.

Secondary Objectives

1. To assess improvement of constipation symptoms in pediatric patients with functional constipation that have been provided a constipation action plan and educational information

Outcome measures: symptoms

Assess constipation symptoms by using the constipation/adherence questionnaire involving ROME IV Criteria at enrollment (with demographics), 1 month telephone encounter and 3 month follow up visit.

2. To assess the perceived effectiveness of the constipation action plan from the viewpoint of the family

Outcome measures: perceived effectiveness of the constipation action plan

Assess the perceived effectiveness by an anonymous survey

Study design/methodology

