This is a randomized controlled single blind study to measure compliance and outcomes in pediatric patients diagnosed with functional constipation. Participants will be recruited from the Division of Pediatric Gastroenterology and Nutrition at Nemours/A.I. duPont Hospital for Children who are being seen with a complaint of constipation. Children are eligible to participate in the study if they are otherwise healthy children whose primary language is English with no conditions that would predispose them to develop constipation, between the ages of 3 and 8 years old and meet the ROME IV criteria for functional constipation. We will obtain parental permission and assent from children older than 7 years of age from all participants. Each family will receive a randomized packet containing educational information (i.e. definitions, water and fiber intake, toilet sitting and medication information), rewards charts and stickers and half of the families will receive an additional constipation action plan tool. The treatment plan for each participant will be determined based on recommendations from the clinical guidelines for the Evaluation and Treatment of Functional Constipation Infants and Children as published by the North American Society for Pediatric Gastroenterology, Hepatology and Nutrition. The packets containing the additional constipation action plan tool will not be known to the investigator prior to assigning the packet to a family. At the first visit, the families will complete an initial paper questionnaire regarding symptomatology, adherence to the treatment plan and demographics. The questionnaires will not contain any patient identifiers and will be stored securely at Nemours. At 1 month, the co-investigator will call each family and administer a phone survey through REDcap regarding symptomatology and adherence to the treatment plan in the past month. At 3 months, the families will return for a follow up visit with their 3 month reward charts and complete a final paper survey regarding the child's symptomatology and adherence to the treatment plan. The CO-I will upload the questionnaire responses onto REDcap based on the identification number. The families who were randomized into the group that received the constipation action plan tool will be mailed a survey regarding the utility of the constipation action plan and whether or not it was helpful in improving adherence to treatment and outcomes. Once received, the feedback survey will also be uploaded onto REDcap based on the identification number.

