
Study Schedule

Children will be recruited from November 2016 - October of 2017. Participants will remain in the study for a total of 3 months, or until the '3-month follow up appointment' is completed, but no later than February 2018.

Adverse Event Reporting

All adverse events and serious adverse events in association with this study will be reported immediately to the IRB. An adverse event is defined as any unfavorable medical occurrence in a human subject, including any abnormal sign (abnormal physical exam or laboratory finding), symptom, or disease, temporally associated with the subject's participation in the research, whether or not considered related to the subject's participation in the research. The AE or SAE will be documented in the online secure database and the participant will have the opportunity to withdraw from the study if warranted, further follow up and monitoring will be scheduled as indicated based on the adverse event.

Statistical Analysis Plan

[figure not shown]
Descriptive statistics will be used to determine the distribution of key outcome and predictor variables. Means and standard deviations will be calculated to describe the distributions of continuous variables. Counts and proportions will be calculated to describe the distributions of categorical variables. The effectiveness of the constipation action plan tool will be assessed by comparing the parent/survey-responder's reported adherence of the child to the constipation treatment in the intervention and control groups, at each follow-up survey, using multivariable logistic regression model. The change in effectiveness of the constipation action plan tool will be assessed by comparing the intervention and control groups across waves of the follow-up surveys, using multivariable mix-effects logistic regression model. Differences in demographic characteristics between the groups will be adjusted for during analysis. The association between compliance and constipation outcomes will be examined likewise.

Informed Consent Process

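### The compliance–symptom analysis adjusts only for demographics; enrolment symptom severity, which is collected, and study arm are not named as covariates for this non-randomised exposure

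*Combined protocol and SAP*

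**What the plan says.** The Statistical Analysis Plan compares reported adherence "in the intervention and control groups, at each follow-up survey, using multivariable logistic regression model", and assesses change over time by "comparing the intervention and control groups across waves of the follow-up surveys, using multivariable mix-effects logistic regression model". It then gives its one adjustment rule: "Differences in demographic characteristics between the groups will be adjusted for during analysis". The next and last sentence is "The association between compliance and constipation outcomes will be examined likewise". No separate covariate list or model is given for that final analysis.

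Symptoms at entry are recorded. Under Study design/methodology, at the first visit "the families will complete an initial paper questionnaire regarding symptomatology, adherence to the treatment plan and demographics", so symptoms and demographics are separate items. Under Secondary Objectives, symptoms are assessed with a "questionnaire involving ROME IV Criteria at enrollment (with demographics), 1 month telephone encounter and 3 month follow up visit". No section names enrolment symptoms or study arm as a covariate in the compliance–symptom analysis.

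**The concern.** The adjustment rule follows two sentences about the randomised arms, where demographic imbalance arises only by chance. The final sentence applies the same approach to compliance, which is behaviour reported by the family after randomisation. The variables that matter there are those that differ between compliant and non-compliant children and also predict later symptoms. How constipated the child was at enrolment is an obvious candidate. Families of sicker children might find the regimen harder to keep, or might be more motivated to keep it.

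Study arm is a second candidate. The tool is meant to raise compliance, and it tells families how to respond to daily symptoms, so it might also act on symptoms by a route that the adherence questions do not capture.

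In the readable text of the Statistical Analysis Plan this is the only inferential analysis that uses the symptom data. A reader of the results could take it as evidence on whether adherence helps.

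**Working it through.** **1. What the rule covers.** In the two sentences before the rule, the groups are the intervention and control arms. Carried over to compliance, the phrase could instead mean compliant and non-compliant families. On either reading the rule covers demographics only, and the first-visit questionnaire lists symptoms apart from demographics. Enrolment severity is therefore unnamed on both readings.

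**2. No figure to reproduce.** The documents give no sample size, significance level, expected adherence or effect size. What follows is illustration under stated assumptions.

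**3. Severity omitted, continuous model.** Let S be enrolment severity, standard normal; C compliance; Y persisting symptoms at follow-up. Assume logit P(C=1|S) = aS and logit P(Y=1|S) = bS. There is no C term in the model for Y, so the true odds ratio (OR) is 1. Without S in the analysis,

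P(Y|C=1) = E[c(S)y(S)] / E[c(S)] and P(Y|C=0) = E[(1−c(S))y(S)] / E[1−c(S)],

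where c(S) and y(S) are the two probabilities above. Numerical integration over S gives, with half the children compliant:

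| a (sicker adhere less) | b | P(Y\|C=1) | P(Y\|C=0) | OR | OR if a is positive |
|---|---|---|---|---|---|
| −0.25 | 0.25 | 0.492 | 0.508 | 0.94 | 1.06 |
| −0.5 | 0.5 | 0.472 | 0.528 | 0.80 | 1.25 |
| −0.5 | 1.0 | 0.451 | 0.549 | 0.67 | 1.48 |
| −1.0 | 1.0 | 0.413 | 0.587 | 0.50 | 2.02 |

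Check of the last row: (0.413/0.587) / (0.587/0.413) = 0.7036² = 0.50. With S in the model the OR is 1.00 by construction; simulations that added severity and arm gave 0.99 to 1.02.

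**4. Cross-check with binary severity.** Here the outcome is improvement, so an OR above 1 looks like benefit. Half the children are severe. Non-severe children have compliance 0.6 and improvement 0.7. If severity multiplies the odds of each by 0.5, severe children have compliance 0.429 and improvement 0.538. Severe children are then 0.417 of compliers and 0.588 of non-compliers. Improvement is 0.633 among compliers and 0.605 among non-compliers, giving a spurious OR of about 1.12. With multipliers 0.33 (compliance) and 0.25 (improvement) it is 1.44. If severe children comply more (multipliers 2 to 3), the OR is 0.89 to 0.70, which looks like harm. The pattern is the same and the sizes are milder than the strongest row above.

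**5. Chance of a false finding.** Sample size is assumed, and the test is two-sided at 0.05 (also assumed). In the strongest row with 100 children, 50 per compliance group, SE = √(2 × 0.413 × 0.587 / 50) = 0.0985, z = 0.174/0.0985 = 1.77, and the rejection probability is Φ(1.77 − 1.96), about 42%. The same formula gives about 28% at 60 children and 70% at 200. In the weakest row it is about 5 to 6% at all three sizes, essentially nominal.

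**6. Arm omitted.** If the tool multiplies the odds of compliance by 1.5 to 3 and, by another route, the odds of improvement by 1.5 to 3, the spurious OR for improvement is 1.04 to 1.33. It is exactly 1.00 if either path is absent.

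**7. Measurement error.** If severity is measured with 70% reliability, adjustment moves the worst case from 0.50 only to 0.76.

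**The case against.** - **Not named is not the same as excluded.** A reader might infer that the plan keeps severity and arm out of the model. The documents do not support that: the models are called multivariable, no covariate list is given, and one figure in the Statistical Analysis Plan is not shown. What stands is that the only stated rule does not name these variables, so their inclusion is left to a later choice.
- **Balanced arms need not mean no adjustment.** That inference requires the groups to be the arms. If they are compliant and non-compliant families, demographics would still be adjusted for. The gap on symptom severity remains on both readings.
- **The analysis is not a listed objective, and the plan calls it an association.** This is correct. No passage commits the sponsor to a causal claim, which limits the weight of the point.
- **Every child meets Rome IV at entry.** This may narrow the range of severity and so weaken confounding. It also means Rome IV status is constant at baseline and cannot serve as the covariate. The documents define no symptom score, so a graded item must be chosen.
- **Arm may not confound.** Following the tool's instructions may itself be compliance, so a separate path to symptoms is plausible but not shown. A tool that helps both compliance and symptoms would bias only towards apparent benefit. The large ORs in the table come from severity alone.

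**Conclusion.** The point holds as a gap in specification with a plausible bias. The analysis of a non-randomised exposure rests on a demographics-only adjustment rule, while a baseline confounder that is already collected goes unnamed.

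Under a null adherence effect and assumed severity effects of 0.25 to 1.0 log-odds per SD, the OR for persisting symptoms runs from about 0.94 to 0.50, or from about 1.06 to 2.0 if sicker children adhere more. These figures depend wholly on the assumptions. At the weak end the distortion is negligible, and nothing in the documents says where this trial lies. Arm is a conditional, secondary reason for adjustment.

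The point concerns only the compliance–symptom association. It does not affect the validity of the randomised comparison of adherence. It is worth correcting because the remedy is nearly free.

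**What to change.** Replace the closing sentence of the Statistical Analysis Plan with:

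> Models of the association between compliance and constipation symptoms include enrolment symptom severity (graded symptom items of the enrolment questionnaire, such as stool frequency or number of Rome IV criteria met, not Rome IV status, which all children meet at entry), study arm and the enrolment demographics, fixed in advance and regardless of differences between arms. Results are reported as observational associations.

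The questionnaire is not reproduced in the documents, so the sponsor should confirm which graded items it holds and name one before the data are examined. No new visit should be needed: symptoms and demographics are recorded at enrolment and arm is known from the packet.

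The cost is wording and a few degrees of freedom; with no stated sample size, the number of demographic terms should be kept modest. Error in the severity measure would leave some confounding. Adherence and symptoms are reported in the same survey, so reverse causation is untouched by this change.

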Informed consent will be taken after the patient is seen in the outpatient setting and has agreed to participate in the study. The CO-I will discuss the project details with the family and allow them to return on a subsequent visit to sign the consent and fill out the forms if they feel they require more time to think about participation. The families will be allowed to ask questions regarding the project and all questions will be answered prior to signing the consent form. The families will meet with the CO-I; all information will be provided to the families including a detailed description of the study and an explanation of how this will contribute to the scientific community. Assent will be obtained from all children 7 years of age and above. We will follow the families at 1 month and at 3 months to complete questionnaires and discuss their continued participation in the study. If the families decide they no longer wish to participate in the study they will be withdrawn. Translations will be submitted to the IRB for review and approval before enrolling non-English speaking participants.

Privacy and confidentiality

Each family will be seen in a private room for the visit encounters. In addition, the follow up surveys are completed via private telephone encounters and follow up interviews in private rooms. The CO-I will organize the list of participants and subsequent study identification numbers (as indicated on each packet they will receive) on password protected computer files (excel spreadsheet) on the Nemours server. The excel spreadsheet will be the only document containing PHI. All printed questionnaires are void of PHI and will contain only a participant (ID) number. The CO-I will upload the questionnaires to a secure website (REDCap) using the appropriate participant ID.

For questions or problems, call:

Name: _____

Phone: _____

Constipation Action Plan

To be completed by your child's doctor or nurse so that you know how best to manage your child's constipation

Doing Well: Stools every 1-2 days No straining or pain Stool is soft
	
Daily Medicine Name: Dose: How Often: **Continue stool softeners, high fiber diet, increased fluid intake, exercise and scheduled toilet breaks everyday.
	
Notes:

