
Constipation worsening: No stool in 2-3 days some pain, or hard stools
	
In addition to your Green Zone medicine, you can:
 
 • Increase your: • If your symptoms do not return to the GREEN zone after 3 days of treatment then add: 	
Notes:

Pay attention: More than 3 stools each day
	
Does child seem to have GI illness (fever, vomiting, watery stools, diarrhea)? Stop constipation medicines for 3 days or until diarrhea resolves -Call doctor for: Refusing liquids, dark urine, loose stools for ___ days
 
No fever, vomiting or signs of illness? Change daily medicine: Dose How often:
	
Notes:

Alert! no stool in 5 or more days Stomach pain, vomiting,
	
 • First, Take: • Second, call your doctor now for help 	
Notes:

Adapted from Stafford B, Wills H, Punati J, Deavenport A, Yin L. Constipation Action Plan. (C) 2012 Children's Hospital Los Angeles. All Rights Reserved

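### Does the action plan tell the family of a vomiting child both to stop and to take constipation medicine?

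*Combined protocol and SAP*

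**What the plan says.** The Constipation Action Plan form, printed at the end of the document, is the randomised intervention. Under Study design/methodology, half of the families receive it in addition to the education packet and reward charts. The form is headed "To be completed by your child's doctor or nurse", and its medicine fields are blank. Three of its rows matter here.

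- **Worsening row.** The trigger is "Constipation worsening: No stool in 2-3 days some pain, or hard stools". The family increases an item left blank, and then: "If your symptoms do not return to the GREEN zone after 3 days of treatment then add", again followed by a blank.
- **Pay attention row.** The trigger is "Pay attention: More than 3 stools each day". The row then asks about illness: "Does child seem to have GI illness (fever, vomiting, watery stools, diarrhea)? Stop constipation medicines for 3 days or until diarrhea resolves". Its reasons for calling the doctor are "Refusing liquids, dark urine, loose stools for" a blank number of days. A second branch, for a child with no fever, vomiting or other sign of illness, changes the daily medicine.
- **Alert row.** The trigger cell reads "Alert! no stool in 5 or more days Stomach pain, vomiting", then a comma, and the extracted text ends there. The first step is a Take line with nothing filled in. The second is "Second, call your doctor now for help".

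**The concern.** Families use this form at home, reading the day's symptoms against the rows. Vomiting is pre-printed in two of them. One row stops constipation medicines; the other begins with taking something. The Alert cell shows no connecting word between its items, and no rule says which row prevails when two apply.

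If the Alert items are alternatives, a vomiting child with frequent stools falls in both rows. The call to the doctor comes after the taking, so it would not settle the matter in time. The Pay attention row's own list of reasons to call does not include vomiting.

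The opposite reading seems to have its own fault. If Alert needs pain or vomiting on top of five stool-free days, a child with five such days and no other symptom is outside Alert, while the worsening row names only two to three days. The form would then look defective however it is read. At stake would be the safety of children in the intervention group and the clarity of the tool under test.

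**Working it through.** The plan gives no figure to reproduce. The check is a comparison of trigger cells and action cells on the form.

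**Inputs.** Let D be no stool for five or more days, P stomach pain and V vomiting, all from the Alert cell. The Pay attention row requires more than three stools a day, which makes D false. The child of interest therefore has D false and V true, with P either way.

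**Step 1: when do both rows apply?**

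| Reading of the Alert cell | Without pain | With pain | Both rows can apply? |
|---|---|---|---|
| D or P or V | Alert | Alert | yes |
| D or (P and V) | not Alert | Alert | yes, with pain |
| D and (P or V) | not Alert | not Alert | no |
| D and P and V | not Alert | not Alert | no |

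Two of the four readings allow the overlap. The documents give no basis for weighting the readings, so this count is not a probability. It describes what a damaged cell leaves open. The trailing comma means that a connecting word, a line break or further symptoms may have been lost when the table was read, and such a loss cannot be charged to the form.

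**Step 2: are the two actions opposed where both rows apply?** The Pay attention row names constipation medicines. The Alert row's Take line names nothing. The actions are opposed only if the doctor or nurse enters a constipation medicine there. That is plausible on such a form, but it is an assumption.

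**Step 3: does the joint reading leave a child with no instruction?** Take a child with D true and neither pain nor vomiting. Under the last two readings this child is not in Alert. But a child with no stool on day 5 already entered the worsening row on day 2 or 3, and that row stays in force until symptoms return to green. Its further step comes after three days of treatment:

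- counting three elapsed days: 2 + 3 = day 5, or 3 + 3 = day 6;
- counting the entry day as the first: 2 + 2 = day 4, or 3 + 2 = day 5.

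The step falls between day 4 and day 6, so the worsening row still governs around day 5 and the child has a printed instruction. The joint readings therefore show neither the overlap nor a missing instruction.

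**Step 4: does anything statistical depend on it?** The Statistical Analysis Plan section compares parent-reported adherence between groups by logistic regression at each follow-up survey and by a mixed-effects model across surveys. It examines the link between compliance and outcomes in the same way. None of these analyses uses the row a family was in.

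**The case for a change.** The strongest case for acting is that a parent cannot tell how the Alert items combine. The form is not uniform: the Doing Well items naturally hold together, while the worsening row prints an explicit alternative. Completion by a clinician does not clearly cure this, because vomiting is pre-printed in both rows and a single Take entry, written before any episode, serves every Alert trigger. A form for managing constipation will probably have a constipation medicine in that blank. Rewording one page is cheap.

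Part of this stands. The extracted text does not settle the Alert trigger, and the blank may well be filled as supposed. But the alternative reading borrows its connecting word from another row. The two opening triggers, frequent stools and prolonged absence of stools, point to rows meant for different situations. The form also has a Notes field in each row, and a name and telephone number for questions or problems are printed just above its heading. These do not prove that the overlap is resolved, but they weaken the claim that completing the form cannot resolve it. The argument that every reading is defective fails at Step 3.

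**Conclusion.** No change to the plan follows. Vomiting does appear in two rows, but a conflict needs two further facts that the documents do not show: that vomiting without five stool-free days triggers Alert, and that the blank Take line holds a constipation medicine. Two of four readings permit the overlap and two exclude it. The documents do not say how often such a child would occur, and no figure, analysis or conclusion of the trial changes.

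This is missing detail on a form completed for each child, seen through a damaged extraction; it is not a demonstrated wrong rule. A query is reasonable: look at the original form and see how the Alert items combine. If vomiting alone is a trigger there and the Take line holds a constipation medicine, the two rows overlap for a vomiting child with frequent stools, and the clinical investigators must reconcile them. Which action applies is theirs to decide, and this review takes no view on it. Confidence that there is a true conflict is low, because it rests on text that may be incomplete.
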